## **6.7 BASELINE, TIME WINDOWS AND CALCULATED VISITS**

Baseline is defined as the last non-missing value recorded prior to first drug administration and is typically collected at visit 2 (day 1). If visit 2 data is missing, visit 1 data will be used (if available). A large black rectangular box used to redact sensitive information.

Planned and actual test days are included in the analysis data sets and are calculated relative to the beginning of treatment as indicated in

[Table 6](#) below.

For efficacy measurements, only one observation per time window will be selected for statistical analysis – the closest one to the planned day in the corresponding time window. If there are two observations which have the same difference in days to the planned day, or if there are two observations on the same day, the first value will be selected. If an observation is available on the last day of treatment, this observation will be preferably selected over any later observation that is still within the time window. Assignment of efficacy observations to visits based on time windows will be based on the non-imputed (observed) data. Repeated and unscheduled efficacy measurements will be assigned to the nominal visits according to the time windows described in

[Table 6](#).

For safety measurements, data collected at all visits will be used. For repeated and unscheduled safety measurements for the same visit on treatment, the worst of these will be

selected for analysis. In the case for which there is no standard reference direction for the safety parameter, the average of all values for the same visit will be used for analysis.

Table 6      Planned study days and analysis time windows

Planned visit	Relative to treatment start	
	Planned test day	Analysis time windows
2	1	Up to Day 1
3	8	Day 2 – Day 13
4	15	Day 14 – Day 20
5	22	Day 21 – Day 27
6	29	Day 28 – Day 34
7	36	Day 35 – Day 41
8 / EOT	43 for completed patients	Day 42 – treatment stop date (stopdt) + 7 days
eEOT	N/A (for early discontinued patients)	Date of the last administration of trial medication + 7 days (for early discontinued patients).  The number of days will be assigned to the visit. Thus, if days to eEOT is 35, it will be mapped to Visit 7. For those who discontinue treatment early but continue with the collection of efficacy data, those data points will be mapped to the later visits as per the above visit window. Hence, if this same patient collects MADRS at Day 36, it will be mapped to Visit 7.
End of Trial	stopdt + 28 days	(stopdt + 8 days) to study end

- Days are counted relative to the day of treatment start, which is defined as Day 1.
- stopdt stands for treatment stop date.

There is no visit window mapping for C-SSRS given that it is collected every week throughout the study.

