#### 7.2.5 Safety analyses

Adverse events will be coded using the Medical Dictionary for Drug Regulatory Activities (MedDRA). Standard BI summary tables and listings will be produced. All adverse events with an onset between start of treatment and end of the REP, a period of 28 days after the last dose of trial medication, will be assigned to the on-treatment period for evaluation.

All treated participants, i.e. all participants in the TS, will be included in the safety analysis. In general, safety analyses will be descriptive in nature and will be based on BI standards. No hypothesis testing is planned.

Statistical analysis and reporting of adverse events will concentrate on treatment-emergent adverse events, i.e. all adverse events occurring between start of treatment and end of the REP. Adverse events that start before first drug intake and deteriorate under treatment will also be considered as 'treatment-emergent'. Adverse event data will be summarized by treatment taken at the onset of the event.

[figure not shown]
Frequency, severity, and causal relationship of adverse events will be tabulated by system organ class and preferred term after coding according to the current version of the Medical Dictionary for Drug Regulatory Activities (MedDRA) at the time specified in the database lock process.

Laboratory data will be analysed both quantitatively as well as qualitatively. The latter will be done via comparison of laboratory data to their reference ranges. Values outside the reference range as well as values defined as clinically relevant will be summarised. Treatment groups will be compared descriptively with regard to distribution parameters as well as with regard to frequency and percentage of participants with abnormal values or clinically relevant abnormal values. Laboratory values of particular interest include:

- c. Low values of HDL, haemoglobin, and neutrophil count
- d. High values of triglyceride levels, total cholesterol, blood glucose, eosinophil count, ALT and GGT

Vital signs, physical examinations, or other safety-relevant data observed at screening, baseline, during the course of the trial and at the end-of-trial evaluation will be assessed with regard to possible changes compared to findings before start of treatment.

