## **7.8 SAFETY ANALYSIS**

All safety analyses will be performed on the TS. Adverse events (AEs) will be coded based on the most current version of MedDRA. Analyses will be performed as defined in CTP Section 7.2.5.

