#### **7.8.2      Laboratory data**

The analyses of laboratory data will be descriptive in nature and will be based on BI standards ([16](#)). Only patients with at least one available on-treatment value will be included in the analysis of an individual laboratory parameter. All individual data will be presented in listings. Study visits will be presented by the Visit labels in [Table 6](#).

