#### **7.8.3      Vital signs**

Only descriptive statistics are planned for this section of the report. In case of multiple measurements including unscheduled visits, the value for the vital sign measurement will be the average of all the measurements for the corresponding visit.

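### Averaging repeat safety values (SAP 6.7 and 7.8.3) can remove a two-sided laboratory abnormality from the out-of-range summaries and a measured extreme from the vital-sign minimum or maximum

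*SAP*

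**What the plan says.** SAP 6.7 sets a general rule for safety data: "For repeated and unscheduled safety measurements for the same visit on treatment, the worst of these will be" the value selected. It then makes an exception: "In the case for which there is no standard reference direction for the safety parameter, the average of all values for the same visit will" enter the analysis.

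SAP 7.8.3 has its own rule for vital signs, with no worst-value provision. When there are several measurements, unscheduled visits included, "the value for the vital sign measurement will be the average of all the measurements for the corresponding visit".

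SAP 7.8.2 gives no repeat-value rule for laboratory data. It says: "The analyses of laboratory data will be descriptive in nature and will be based on BI standards". That standard is cited but is not part of the documents.

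On output, SAP 7.8 points back to the protocol: "Analyses will be performed as defined in CTP Section 7.2.5". The laboratory paragraph of protocol 7.2.5 commits to this: "Values outside the reference range as well as values defined as clinically relevant will be summarised". No readable text exempts these summaries from the averaging rule in SAP 6.7.

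**The concern.** Extra measurements are not a random sample of a participant's values. Protocol 6.1 allows added visits for laboratory re-testing or AE monitoring, and protocol 6.2.1 allows unscheduled visits to check a participant's safety. Averaging therefore acts largely where something had already caused concern, and it mixes the worrying value with its follow-up.

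The worst-value rule shows that the SAP does not want a recheck to hide an abnormal result. A parameter that can be abnormal at both ends needs that protection twice, for the lowest and for the highest value. Under the exception it gets neither, and the number compared with the reference range may be one that was never measured.

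At stake is whether the by-arm laboratory summaries show every out-of-range result for such parameters, and whether the vital-sign tables show the extremes actually recorded. This is a first-in-class compound, and protocol 2.1.1 uses safety data to support dose selection.

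**Working it through.** The plan states no figure to reproduce, because this is a data-handling rule. The check has four steps.

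**1. Which rule applies where**

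| Data | Rule as written | Planned summary |
|---|---|---|
| Laboratory, one bad direction | worst value (SAP 6.7) | out-of-range and clinically relevant values (protocol 7.2.5) |
| Laboratory, no single direction | average (SAP 6.7), unless the sponsor's standard differs | same |
| Vital signs | average (SAP 7.8.3) | descriptive statistics, including minimum and maximum (SAP 7) |
| ECG | not relevant | no quantitative analysis (SAP 7.8.4) |

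The SAP does not list the tests without a direction. Sodium, potassium and calcium are in the panel (protocol Table 5.3.3:1) and are natural candidates, but that classification is an assumption.

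**2. When an abnormal value disappears**

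Let the abnormal value lie d above an upper limit L, and let k rechecks have mean r. The average is (L + d + k·r)/(k + 1). It is at or below L exactly when r ≤ L − d/k. The lower limit is the mirror image.

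Examples with assumed values and limits, none taken from the documents:

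- Potassium, range 3.5 to 5.1: (3.0 + 4.2)/2 = 3.6, in range. (5.8 + 4.2)/2 = 5.0, in range. (5.8 + 4.6)/2 = 5.2, still high.
- Sodium, lower limit 135: (130 + 140)/2 = 135, in range. (130 + 138)/2 = 134, still low.
- Systolic pressure: (84 + 120)/2 = 102. The measured 84 cannot appear as the reported minimum.

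So an abnormal value can be lost, but not always. Where the average stays abnormal, the extreme is still understated.

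**3. How often, among values that are rechecked**

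Assume standard normal values, limits at ±1.96 SD, one recheck and within-person correlation ρ. The quantity simulated is P(|(X1 + X2)/2| ≤ 1.96, given |X1| > 1.96).

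| ρ | Share returned to range |
|---|---|
| 0.4 | 0.741 |
| 0.6 | 0.592 |
| 0.8 | 0.393 |

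A separate simulation with an upper limit only also gave 39% at ρ = 0.8.

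**4. How often, among all out-of-range values**

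The documents give no recheck rate. Multiplying the shares above by an assumed rate:

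- 10% rechecked: 0.10 × 0.393 = 3.9% to 0.10 × 0.741 = 7.4%, about 4% to 7%.
- 25% rechecked: 0.25 × 0.393 = 9.8% to 0.25 × 0.741 = 18.5%, about 10% to 19%.

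If individual lowest and highest values feed the summaries, none is lost.

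**The case against.** The case on the other side has real force.

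- **The laboratory part depends on an unseen standard.** It may already say which value enters the abnormality tables. This stands, so the laboratory conclusion is conditional. If the standard does differ, SAP 6.7 still needs a cross-reference, because as written it governs.
- **The values the protocol singles out are protected.** Protocol 7.2.5 lists its laboratory values of particular interest with a direction (for example low haemoglobin, high ALT), so the worst value is kept. The hepatic AESI is defined on elevations. This stands.
- **Measured values are not destroyed.** They stay in listings (SAP 7 and 7.8.2). Changes the investigator judges clinically relevant become AEs (protocol 5.3.3 and 5.3.6.1.1), and the DMC sees laboratory data (protocol 3.2). This reduces the harm. It does not replace the summaries, since listings give no counts by arm and AE capture depends on judgement.

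A reader might infer that abnormal vital signs will be under-counted. The documents do not support that. The out-of-range commitment is in the laboratory paragraph of protocol 7.2.5, and no readable text plans an abnormal-count table for vital signs.

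A reader might also infer that the between-arm comparison is biased towards no difference. That is plausible if one arm has more rechecks, but no two-arm calculation was made and the documents give no recheck rates by arm. Using extremes has an opposite weakness: participants checked more often have more chances to show one.

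**Conclusion.** The point holds in a limited form. As written, the averaging in SAP 6.7 can turn a measured abnormality into an in-range value for laboratory parameters without a single bad direction, and so remove it from summaries that protocol 7.2.5 promises. This assumes that the sponsor's laboratory standard sets no other rule and that tests such as sodium or potassium are classed as having no direction. For vital signs, SAP 7.8.3 can leave a measured extreme out of the reported minimum or maximum.

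The size is uncertain. The 39% to 74% range should not be read as the share of all abnormal values lost: it applies only to values that are rechecked. It also describes chance excursions, since the simulation contains no drug effect. Safety analysis is descriptive with no hypothesis test, so no decision rule changes.

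**What to change.** In SAP 6.7, limit averaging to by-visit descriptive means. State that out-of-range, clinically relevant and shift summaries use individual measured on-treatment values, taking both the lowest and the highest for parameters that can be abnormal either way. Name the parameters that count as having no direction. If the laboratory standard already requires individual values, cite it in 6.7. The worst-value rule for one-directional parameters can stay as it is; there is no need to restrict all by-visit means to scheduled measurements.

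In SAP 7.8.3, report by arm each participant's lowest and highest measured on-treatment blood pressure and pulse, taken from individual values.

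The cost is SAP wording and a little programming, with no new data. Abnormal counts will be slightly higher. A table footnote should say that participants with more unscheduled checks have more chances to show an extreme.

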**Option 1:** An early EoT Visit must be conducted within 7 days of the last dose of trial medication for participants who agree to conduct regularly scheduled visits after premature drug discontinuation (if consistent with the planned visit schedule, the eEOT can replace the next regularly scheduled clinic visit). After this early EOT visit, participants should be followed up according to the regularly scheduled visit for both clinic and phone visits until Visit 8 and must complete the FUP Visit 28+2 days after the drug discontinuation date. All procedures should be completed, with the exception of trial drug procedures and [REDACTED]. If FUP visit (early drug discontinuation date + 28+2 days) can be completed prior to the date of the planned Visit 8, no additional FUP is needed. However, end of study participation must be completed.

**Option 2:** An early EoT Visit must be conducted within 7 days of the last dose of trial medication. If the participant is not willing to return for all regularly scheduled visits, at a minimum they must return for Visit 8 and FUP. If FUP visit (early drug discontinuation date + 28+2 days) can be completed prior to the date of the planned Visit 8, no additional FUP is needed. However, end of study participation must be completed.

1 Prior to any trial related procedure, may also be done at an extra visit up to 2 weeks before V1.

2 Urine drug screen at screening visit only. For WOCBP, a serum pregnancy will be performed at screening and a urine pregnancy tests at all clinic visits beginning with V2. If a urine pregnancy test is positive, a serum test needs to be performed for confirmation.

3 Participants will bring trial medication (used/unused blister and covering packages) to site visits for compliance check (V3/V4/V6/V8) and for resupply (V4 and V6). Participants have to take the morning dose of the IMP, at the trial site at all clinical visits, except EOT at Visit 8 also to allow [REDACTED]. Last regular intake of the trial drug is the day before EOT visit. Please refer to footnote 4.

[REDACTED]

[REDACTED]

[REDACTED]

7 After the EoStudy visit (= individual participant's end of the trial) the investigator should report only any cancers of new histology and exacerbations of existing cancer, trial treatment related SAEs and trial treatment related AESIs of which the investigator may become aware of and only via the BI SAE form, please see section [5.3.6.2.1](#).

8 Telephonic Visit

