#### Participants prematurely discontinuing trial drug

Participants who discontinue trial drug prematurely should ideally be observed until trial end as if they were still receiving blinded trial treatment. If this is not possible, then participants should be encouraged to come back to the site and complete week 6 visit procedures, with the performance of the MADRS scale as a minimum requirement. See section [Flow Charts](#) and [3.3.4.](#) for further options.

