### 7.3 HANDLING OF MISSING DATA

Every effort will be made to collect complete data at all visits.

The primary estimand of interest is the treatment effect assuming all participants remain adherent to the assigned trial medication and trial protocol using a hypothetical approach. For the primary analysis of the primary endpoint, missing data will not be imputed. Data collected after discontinuation of trial medication will be censored for the primary analysis. The mixed effects model will handle missing data based on a likelihood method under the assumption of missing at random.

For the supplemental analysis of the primary endpoint based on a treatment policy estimand, i.e. intention to treat, all available data including data collected after treatment discontinuation or other intercurrent event will be analysed.

Similar methods for handling missing data will be used for secondary efficacy endpoints, as applicable.

With respect to safety evaluations, it is not planned to impute missing values.

More details for missing data handling will be included in the TSAP, if needed.

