#### MMRM analysis

The change from baseline in MADRS total score at Week 6 for each dose group as well as the corresponding variance-covariance matrix will be estimated by an MMRM model including the fixed categorical effects of treatment at each visit, concomitant psychotherapy use (yes vs. no), and the fixed continuous effect of baseline MADRS total score at each visit. Visit will be treated as a repeated measure with an unstructured covariance matrix used to estimate within patient error variability. The Kenward-Roger approximation will be used to estimate the denominator degrees of freedom and adjust standard errors. Significance tests will be based on least-squares (LS) means using a two-sided  $\alpha = 0.1$  (two-sided 90% confidence intervals (CIs)). Analyses will be implemented using SAS 9.4 PROC MIXED.

More specifically, the change in MADRS total score from baseline at Visits 3, 4, 6, and 8 (Weeks 1, 2, 4, and 6) will be evaluated using an MMRM accounting for the following sources of variation: ‘concomitant psychotherapy use’, ‘treatment\*visit’ interaction, and ‘baseline MADRS total score\*visit’ interaction as fixed effects, and visit as a repeated measure within each patient. The methods described in [Section 10.1.1](#) will be utilized to resolve model non-convergence.

The following SAS code will be used to run the MMRM model, with some modifications if necessary:

```
PROC MIXED DATA=indata cl method=reml;
  CLASS visit trt(REF='placebo') ptno conPTuse;
  MODEL aval = conPTuse visit*trt base*visit / ddfm=kr s;
  REPEATED visit / subject= ptno type=un r rcorr;
  LSMEANS visit*trt / pdiff=all om cl alpha=0.10 slice=visit;
RUN;
```

Results of the MMRM (N, LS means, standard errors, and 90% CIs per dose group) will be presented in tables and displayed graphically.

Descriptive summaries for observed values and change from baseline in MADRS total score at Weeks 1, 2, 4 and 6 will be presented by treatment arm, including the quetiapine arm. The frequency and proportion of participants reporting each response category for each MADRS item at baseline and up to Week 6 will also be displayed.

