#### **7.4.3        Supplementary analysis**

An additional analysis of the primary endpoint will repeat the primary analysis methodology (MMRM/MCPMod) specified in [Section 7.4.1](#), but under a treatment policy estimand, i.e., effectiveness/intention to treat. This estimand approach will use all available MADRS data, including data collected after any intercurrent event listed in [Table 3](#). As discussed in [Section 6.3](#), an intercurrent event of death will be handled using a hypothetical approach.

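### SAP Table 6 leaves no Week 6 window for participants whose last dose is on or before Day 34, so the treatment-policy MMRM would omit Week 6 MADRS scores collected from them

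*SAP*

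**What the plan says.** SAP Table 6 gives Visits 3 to 7 windows in fixed study days; Visit 7, for instance, is Days 35 to 41. Visit 8 alone has an upper limit that depends on the individual: "Day 42 – treatment stop date (stopdt) + 7 days". The End of Trial row runs from "stopdt + 8 days) to study end". For participants who stop drug early but continue to give efficacy data, the eEOT row says that "those data points will be mapped to the later visits as per the above visit window". Its worked example has an eEOT at Day 35 and a MADRS at Day 36, both mapped to Visit 7.

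The MMRM in SAP 7.4.1 models the "change in MADRS total score from baseline at Visits 3, 4, 6, and 8 (Weeks 1, 2, 4, and 6". SAP 7.4.3 repeats that method for the treatment-policy estimand and states: "This estimand approach will use all available MADRS data, including data collected after any intercurrent event listed in" Table 3. Protocol 7.3 agrees that "all available data including data collected after treatment discontinuation or other intercurrent event will be analysed".

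The protocol also sets out to collect these scores. Section 6.2.1 asks early discontinuers who cannot follow the full schedule to return and "complete week 6 visit procedures, with the performance of the MADRS scale as a minimum requirement". Under Option 2 in Flow Chart 1, "at a minimum they must return for Visit 8 and FUP".

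**The concern.** Last dose plus 7 days is the on-treatment definition of the primary hypothetical estimand (SAP 7.4.1). Table 6 builds that limit into the visit window itself, so it also governs the analysis that is supposed to disregard treatment discontinuation. A participant who stops in Week 3 and comes back on Day 43 gives exactly the score the treatment-policy estimand needs, yet Table 6 labels it End of Trial, and End of Trial is not a visit in the model.

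For those participants Week 6 would be handled implicitly under missing at random although the value exists. Off-treatment scores at Weeks 1, 2 and 4 stay in the model and carry some information, but someone who returns only for Visit 8 has few or none. The expected direction is to pull the treatment-policy result towards the hypothetical one. Agreement between the two would then be weaker evidence of robustness than it appears.

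**Working it through.** **Inputs.** Visit 8 window: Day 42 to stopdt + 7. End of Trial: stopdt + 8 onwards. Visits in the MMRM: 3, 4, 6 and 8. All are from SAP Table 6 and 7.4.1. Visit 8 is scheduled on Day 43 ± 2 and eEOT within 7 days of the last dose (protocol flow charts). Arm sizes are from the protocol synopsis.

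**The plan's own example.** Day 35 and Day 36 both lie in Days 35-41, so both map to Visit 7, as Table 6 says. Now continue the same patient to Week 6. An eEOT on Day 35, within 7 days of the last dose, means stopdt is between 28 and 35. End of Trial then starts between Day 28 + 8 = 36 and Day 35 + 8 = 43. A Day 43 score is End of Trial for every one of these stop dates.

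**When the window exists.** It needs stopdt + 7 ≥ 42, that is stopdt ≥ 35. At stopdt 34 it would run from Day 42 to Day 41.

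| Last dose (stopdt) | Visit 8 window | Day 42 | Day 43 | Day 44 | Day 45 |
|---|---|---|---|---|---|
| Day 34 or earlier | empty | End of Trial | End of Trial | End of Trial | End of Trial |
| Day 35 | Day 42 | Visit 8 | End of Trial | End of Trial | End of Trial |
| Day 36 | Days 42-43 | Visit 8 | Visit 8 | End of Trial | End of Trial |
| Day 37 | Days 42-44 | Visit 8 | Visit 8 | Visit 8 | End of Trial |
| Day 38 or later | Day 42 to at least Day 45 | Visit 8 | Visit 8 | Visit 8 | Visit 8 |

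**Share of stop days affected**, assuming stop days spread evenly over Days 1-41:

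- Day 42 visit: 34/41 = 82.9%
- Day 43 visit: 35/41 = 85.4%
- Day 45 visit: 37/41 = 90.2%

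**Number of scores.** The treatment-policy model covers placebo and the four BI 1358894 arms: 144 + 41 + 41 + 41 + 82 = 349. With p the assumed proportion stopping early and r the assumed proportion of those who return on Day 43, scores lost = 349 × p × r × 35/41.

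| p | r = 1 | r = 0.5 |
|---|---|---|
| 5% | 14.9 | 7.4 |
| 10% | 29.8 | 14.9 |
| 20% | 59.6 | 29.8 |

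If p is instead taken as the proportion stopping by Day 34, with all returning, the range is 349 × 0.05 = 17 to 349 × 0.20 = 70.

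**Check of the remedy.** With a fixed upper limit of Day 45 or Day 49, a Day 43 score maps to Visit 8 for each stop date tried (Days 7, 21, 34 and 35).

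**The case against.** The strongest reply is that the SAP plainly means to keep these data. The Visit 8 row gives its planned day for completers only, early discontinuers have their own row, and SAP 7.4.3 and protocol 7.3 both call for post-discontinuation data. End of Trial is also an odd home for a MADRS score, since Flow Chart 2 schedules none at follow-up. The worked example even suggests that visit windows take precedence: if the last dose was Day 28, Day 36 falls in both Visit 7 and End of Trial, and the SAP chooses Visit 7.

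The intent is granted, but it does not repair the rule. The eEOT row refers back to the windows above it, and for Week 6 that is the capped row. If that row is for completers only, discontinuers have no Week 6 window at all. Precedence over End of Trial cannot help when the Visit 8 window is empty.

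Four points do stand:

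- Parts of the SAP are withheld. Section 6.3 refers to a Section 7.4.5 for estimand detail, which is not readable (it may be a slip for 7.4.3), and the code in Section 10 is not shown. A mapping rule there cannot be excluded; no readable section gives one.
- The counts rest on assumed dropout, return and timing. Full return is a ceiling, because protocol 6.2.1 lets a participant unwilling to continue complete Visit 8 early, in which case there is no Day 43 score to lose.
- The analysis is supplementary, and the proof-of-concept decision does not rest on it.
- A Visit 8 held on Day 41, which the protocol permits, maps to Visit 7 and is also outside the MMRM. A change to the upper limit does not address that.

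**Conclusion.** The concern holds. As written, Table 6 removes collected Week 6 scores from the analysis meant to use them. The limits are exact: no window for a last dose on or before Day 34, the planned Day 43 score lost for a last dose on or before Day 35, and a result that depends on the visit day for Days 35-37. How many scores are affected is uncertain: about 7 to 60 of 349 participants under assumed early stopping of 5-20% and return of 50-100%, with stop days spread evenly. No shift in the effect estimate is claimed.

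The primary analysis is unaffected, because it excludes data beyond last dose plus 7 days in any case. Late discontinuers, and participants still on drug after another intercurrent event, keep their Week 6 score. This should be fixed. Confidence is medium because of the withheld SAP text.

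**What to change.** Reconcile the Visit 8, eEOT and End of Trial rows of Table 6:

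- For the supplementary treatment-policy analysis, define Visit 8 by study day with a fixed upper limit that does not depend on stopdt. Day 49 is one choice, since Table 6 already gives it to a completer with a last dose on Day 42 (42 + 7).
- Give visit windows priority over End of Trial, or start End of Trial after the Week 6 window closes.
- Keep stopdt + 7 only as the censoring rule of the primary estimand.
- Extend the worked example to a Day 43 score from an early discontinuer.

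The cost is a few lines in Table 6 and one visit variable for the supplementary analysis. No new data are needed and the primary analysis does not change.
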